8.2.1. Physical Examinations

A physical examination will be performed at the screening visit and, if clinically indicated, prior to the participant's first vaccination (Visits 1 and 201 for Substudies A and B, respectively). Physical examination findings collected during the study will be considered source data and will not be required to be reported, unless otherwise noted. Any untoward physical examination findings that are identified during the active collection period and meet the definition of an AE or SAE (Appendix 3) must be reported according to the processes in Sections 8.3.1 to Section 8.3.3.

8.2.2. Vital Signs

The participant's body temperature will be measured prior to each vaccination. Additionally, weight, height (at screening), pulse rate, and seated blood pressure will be measured prior to the participants first vaccination.

8.2.3. Electronic Diary

Participants will be required to complete a reactogenicity e-diary after each vaccination through an application installed on a provisioned device or on the participant's own personal device. All participants will be asked to monitor and record local reactions, systemic events, and use of antipyretic medication for 7 days from the day of administration of the study intervention. The reactogenicity e-diary allows recording of these assessments only within a fixed time window, thus providing the accurate representation of the participant's experience at that time. Data on local reactions and systemic events reported in the reactogenicity e-diary will be transferred electronically to a third-party vendor, where they will be available for review by investigators and the Pfizer clinicians at all times via an internet-based portal.

At intervals agreed to by the vendor and Pfizer, these data will be transferred electronically into Pfizer's database for analysis and reporting. These data do not need to be reported by the investigator in the CRF as AEs.

Investigators (or designee) will be required to review the reactogenicity e-diary data online at frequent intervals as part of the ongoing safety review.

The investigator or designee must obtain stop dates from the participant for any ongoing local reactions, systemic events, or use of antipyretic medication on the last day that the reactogenicity e-diary was completed. The stop dates should be documented in the source documents and the information entered in the CRF.

8.2.3.1. Grading Scales

The grading scales used in this study to assess local reactions and systemic events as described below are derived from the FDA CBER guidelines on toxicity grading scales for healthy adult volunteers enrolled in preventive vaccine clinical trials.²⁴

8.2.3.2. Local Reactions

During the reactogenicity e-diary reporting period, participants will be asked to assess redness, swelling, and pain at the injection site and to record the symptoms in the reactogenicity e-diary. In Substudy B, local reactions will be assessed at the injection site on the right arm only.

If a local reaction persists beyond the end of the reactogenicity e-diary period following vaccination, the participant will be requested to report that information. The investigator will enter this additional information in the CRF.

Participants will be provided with a measuring device. Redness and swelling will be measured and recorded in measuring device units (range: 1 to 21) and then categorized during analysis as absent, mild, moderate, or severe based on the grading scale in Table 1. Measuring device units can be converted to centimeters according to the following formula: 1 measuring device unit = 0.5 cm. Pain at the injection site will be assessed by the participant as absent, mild, moderate, or severe according to the grading scale in Table 1.

If a Grade 3 local reaction is reported in the reactogenicity e-diary, a telephone contact should occur to ascertain further details and determine whether a site visit is clinically indicated. Only an investigator or medically qualified person is able to classify a participant's local reaction as Grade 4. If a participant experiences a confirmed Grade 4 local reaction, the investigator must immediately notify the sponsor and, if it is determined to be related to the administration of the study intervention, further vaccinations will be discontinued in that participant.

Table 1. Local Reaction Grading Scale

	Mild (Grade 1)	Moderate (Grade 2)	Severe (Grade 3)	Potentially Life-Threatening (Grade 4)
Pain at the injection site	Does not interfere with activity	Interferes with activity	Prevents daily activity	Emergency room visit or hospitalization for severe pain
Redness	>2.0 cm to 5.0 cm (5 to 10 measuring device units)	>5.0 cm to 10.0 cm (11 to 20 measuring device units)	>10 cm (≥21 measuring device units)	Necrosis or exfoliative dermatitis

Table 1. Local Reaction Grading Scale

	Mild (Grade 1)	Moderate (Grade 2)	Severe (Grade 3)	Potentially Life-Threatening (Grade 4)
Swelling	>2.0 cm to 5.0 cm	>5.0 cm to 10.0 cm	>10 cm	Necrosis
	(5 to 10 measuring	(11 to 20 measuring	(≥21 measuring	
	device units)	device units)	device units)	

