- The difference in the proportion of participants achieving seroconversion against 1 week following Vaccination 1 was 29.8%, 27.4%, -8.2%, and 0.0%, respectively, when comparing participants who received qIRV to those who received licensed QIV.

These data support exploration of alternative vaccination schedules incorporating IRV, which are included in Substudy B.

Substudy B will describe the safety and immunogenicity of the following vaccination schedules:

In participants 65 to 85 years of age:

- 2 Doses of qIRV encoding 2 A strains and 2 B strains at a dose level of CC administered 21 days apart.
- 2 Doses of licensed QIV, administered 21 days apart (as a control group).
- A dose of licensed QIV followed by a dose of bIRV encoding 2 A strains at a dose level of either **CC** , administered 21 days apart.
- A dose of licensed QIV administered concurrently in the opposite arm with bIRV encoding 2 A strains at a dose level of either **CC**
- A dose of bIRV encoding 2 A strains at a dose level of CC administered concurrently in the opposite arm with bIRV encoding 2 B strains at a dose level of CC
- A dose of qIRV encoding 2 A strains and 2 B strains at the following dose level combinations:

PFIZER CONFIDENTIAL

• A dose of licensed QIV (as a control group).

In participants 18 to 64 years of age:

- A dose of qIRV encoding 2 A strains and 2 B strains at a dose level of CC
- A dose of qIRV encoding 2 A strains and 2 B strains at a dose level of CCI

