- Enrollment will be controlled for the first group in which the total dose of modRNA vaccine administered at a single vaccination is **CCI**, and also for the first group in which the total dose is **CCI** as follows:
 - No more than 5 participants can be vaccinated on the first day.
 - Vaccination of the remaining participants will commence no sooner than 24 hours after the fifth participant received his or her vaccination.
- Safety and immunogenicity data accumulated at least 1 week following the last vaccination in each group will be reviewed by the sponsor's IRC and, if deemed acceptable, an additional 120 participants 65 to 85 years of age will be enrolled in that group (expanded enrollment).
- If a group is not selected for enrollment expansion or, based on review of immunogenicity data at the 4-week time point, at the sponsor's discretion, subsequent collection of blood samples from participants in that group may be halted and/or not analyzed.

As detailed above, Substudy B expanded enrollment will comprise group(s) of 120 participants following the vaccination schedule(s) as selected by the sponsor's IRC from initial enrollment. Additionally,

• 240 participants 18 to 64 years of age will be randomized 1:1 to receive either a single dose of CCI qIRV (encoding 2 A strains and 2 B strains at a dose level of CCI qIRV (encoding 2 A strains and 2 B strains at a dose level of CCI.).

- Expanded-enrollment groups may also be included that comprise only the first dose from 2-visit—schedule initial enrollment groups, eg, 1 dose of qIRV at a dose level of ...
- At the discretion of the sponsor's IRC, a control group of 120 participants may be enrolled during expanded enrollment who will receive a dose of licensed QIV followed by placebo, administered 21 days apart.

Therefore, Substudy B expanded enrollment will consist of approximately 120 to 1725 participants, depending on the number of groups selected to progress to expanded enrollment.

Stopping rules will apply throughout initial and expanded enrollment as detailed in Section 10.10.8.6.

All participants will be asked to complete a reactogenicity e-diary for 7 days following each vaccination. Blood samples of approximately 50 mL will be collected for immunogenicity assessments prior to Vaccination 1, prior to Vaccination 2 (if applicable), and at 1, 4, and 8 weeks after the participant's last vaccination.

The total duration of the study for each participant will be up to approximately 8 months.

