10.10.6.1.1. Administration

See Section 6.1.1.

During Substudy B, participants will receive study intervention as randomized at Visit 201 and, if applicable, at Visit 203 in accordance with the SoA (Section 10.10.1).

Study intervention should be administered intramuscularly as detailed in Table 6.

 Table 6.
 Substudy B Study Intervention Schedule

Participant	Vaccine	Study Intervention	- Vaccination 1	Study Intervention -	Vaccination 2
Age	Group	Right Deltoida	Left Deltoid	Right Deltoida	Left Deltoid
	1	qIRV CCI		qIRV CCI	
		2 x A, 2 x B		2 x A, 2 x B	
		CCI		CCI	
	2	Licensed QIV		bIRV CCI	
				2 x A CC	
	3	Licensed QIV		bIRV CC	
				2 x A CC	
	4	Licensed QIV		Licensed QIV	
	5	bIRV CC	Licensed QIV		
65.		2 x A CC			
65 to	6	bIRV CC	Licensed QIV		
85 years of		2 x A CC			
age		qIRV CCI			
	7	$2 \times A, 2 \times B$			
		CCI			
	8	Licensed QIV			
		bIRV CC	bIRV CC		
	9		2 x A		
		2 x B CC	CCI		
		qIRV CC			
	10	2 x A CC			
		2 x B CC			

PFIZER CONFIDENTIAL

Table 6. Substudy B Study Intervention Schedule

Participant	Vaccine	Study Intervention - Vaccination 1		ne Study Intervention - Vaccination 1 Study Intervention	Study Intervention -	Vaccination 2
Age	Group	Right Deltoid ^a	Left Deltoid	Right Deltoida	Left Deltoid	
	11	qIRV CCI 2 x A CCI 2 x B CCI				
	12	Licensed QIV			Placebo	
18 to	13	qIRV CCI 2 x A, 2 x B				
64 years of age	14	qIRV CCI 2 x A, 2 x B				

a. Local reactions will be assessed at the injection site on the right deltoid (see Section 8.2.3.2).

Study intervention in Substudy B will be administered in a single-blinded manner.

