10.10.8.3. Safety Assessments

See Section 8.2.

Note, for Substudy B, local reactions will be assessed at the injection site on the right arm only (see Section 8.2.3.2).

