2.2.1. Primary Safety Estimands

The primary estimands for the primary objective will follow the treatment policy strategy from the EMA ICH E9 (R1) addendum¹ and estimate the safety percentages regardless of the occurrence of intercurrent event(s) or rescue medication use. The analyses will be based on the actual vaccine received.

In participants receiving at least 1 dose of study intervention:

• The percentage of participants reporting prompted local reactions up to 7 days following each vaccination.

This estimand includes the following attributes:

- Treatment: 1-Visit schedules or 2-visit schedules with modRNA, licensed QIV, and/or placebo or their combinations as listed in Table 2.
- Population: Safety population for 1-visit schedules and Vaccination 1 safety population or Vaccination 2 safety population for 2-visit schedules as defined in Section 4.
- Variable: Presence/absence of prespecified local reactions up to 7 days after each vaccination.
- Intercurrent event(s): For participants who discontinue receipt of study intervention or discontinue participation in the study.
- Population-level summary: Percentage and associated 2-sided 95% CI of participants reporting local reactions in each vaccine group.
- The percentage of participants reporting prompted systemic events up to 7 days following each vaccination.

- Treatment: 1-Visit schedules or 2-visit schedules with modRNA, licensed QIV, and/or placebo or their combinations as listed in Table 2.
- Population: Safety population for 1-visit schedules and Vaccination 1 safety population or Vaccination 2 safety population for 2-visit schedules as defined in Section 4.
- Variable: Presence/absence of prespecified systemic events up to 7 days after each vaccination.
- Intercurrent event(s): Participants discontinue.

- Population-level summary: Percentage and associated 2-sided 95% CI of participants reporting systemic events in each vaccine group.
- The percentage of participants reporting AEs from the first vaccination to 4 weeks after the last vaccination.

This estimand includes the following attributes:

- Treatment: 1-Visit schedules or 2-visit schedules with modRNA, licensed QIV, and/or placebo or their combinations as listed in Table 2.
- Population: Safety population as defined in Section 4.
- Variable: Presence of AEs from the first vaccination to 4 weeks after the last vaccination.
- Intercurrent event(s): Participants discontinue.

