3.1.1.1. Local Reactions

During the reactogenicity e-diary reporting period, participants will be asked to assess redness, swelling, and pain at the injection site and to record the symptoms in the reactogenicity e-diary. Local reactions will be assessed at the injection site on the right arm only.

If a local reaction persists beyond the end of the reactogenicity e-diary period following each vaccination, the participant will be requested to report that information. The investigator will enter this additional information in the CRF.

Redness and swelling will be measured and recorded in measuring device units (range: 1 to 21) and then categorized during analysis as absent, mild, moderate, or severe based on the grading scale in Table 3. Measuring device units can be converted to centimeters according to the following formula: 1 measuring device unit = 0.5 cm. Pain at the injection site will be assessed by the participant as absent, mild, moderate, or severe according to the grading scale in Table 3.

	Mild (Grade 1)	Moderate (Grade 2)	Severe (Grade 3)	Potentially Life-Threatening (Grade 4)
Pain at the injection site	Does not interfere with activity	Interferes with activity	Prevents daily activity	Emergency room visit or hospitalization for severe pain
Redness	>2.0 cm to 5.0 cm (5 to 10 measuring device units)	>5.0 cm to 10.0 cm (11 to 20 measuring device units)	>10 cm (≥21 measuring device units)	Necrosis or exfoliative dermatitis
Swelling	>2.0 cm to 5.0 cm (5 to 10 measuring device units)	>5.0 cm to 10.0 cm (11 to 20 measuring device units)	>10 cm (≥21 measuring device units)	Necrosis

Presence or Absence

For the data summary of the presence (yes or no) of a local reaction during the interval from Day 1 through Day 7 for each dose, where Day 1 is the day of each dose, the following variables are required in order to compute the proportions:

- Presence (yes or no) of each severe/Grade 4 local reaction on each day and any day (Day 1 through Day 7);
- Presence (yes or no) of each local reaction by maximum severity on any day (Day 1 through Day 7).

For each local reaction and any local reaction on any day, Table 4 details the algorithm to derive the presence of a reaction (yes or no) during the interval from Day 1 through Day 7, where Day 1 is the day of each dose.

Table 4. Derived Variables for Presence of Each and Any Local Reaction Within 7 Days for Each Dose

Variable ^a	Yes (1)	No (0)	Missing (.)

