5.3.1.1. Reactogenicity Data

For derived variables based on reactogenicity data, if any day of the 7-day e-diary is available, the "any day (Day 1-7)" data will be considered nonmissing.

The reactogenicity data are collected through the e-diary, which does not allow participants to skip the question. Therefore, for a specific day, as long as the e-diary data are transferred for that day, all of the reactogenicity data for the participant on that day are nonmissing. No missing reactogenicity data will be imputed other than what is described in Section 3.1.1.1 and Section 3.1.1.2.

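### Substudy B prompts for local reactions in the right arm only, so Group 9's rate misses one of its two modRNA sites and Group 12's post-placebo rate would come from an arm not injected at that visit

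*Protocol*

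**What the plan says.** The restriction appears four times. Protocol 8.2.3.2 has "In Substudy B, local reactions will be assessed at the injection site on the right arm only", and SAP 3.1.1.1 has "Local reactions will be assessed at the injection site on the right arm only". Protocol 10.10.8.3 and footnote a to protocol Table 6 say the same.

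The regimens are set out in protocol Table 6 (10.10.6.1.1):

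- **Group 9** is the schedule in which bIRV encoding 2 A strains is given "concurrently in the opposite arm with bIRV encoding 2 B strains" (protocol 2.1). Table 6 puts the 2 x B product in the right deltoid and the 2 x A product in the left.
- **Group 12** is described in protocol 10.10.4.1: "a control group of 120 participants may be enrolled during expanded enrollment who will receive a dose of licensed QIV followed by placebo". Table 6 puts QIV in the right deltoid at Vaccination 1. At Vaccination 2 placebo stands in the left-deltoid column and the right-deltoid cell is blank. The protocol 1.2.2 schema and SAP Table 2 also show placebo under the left deltoid. No prose names the arm.

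The primary estimand in SAP 2.2.1 is "The percentage of participants reporting prompted local reactions up to 7 days following each vaccination". It is stated per participant and names no arm. SAP 6.1.1.1 tabulates it by vaccine group, using the Vaccination 2 safety population for second doses of 2-visit schedules.

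**The concern.** Local reactions are a primary safety endpoint. For Group 9 the tabulated rate is valid for the 2 x B site but is silent on the other modRNA injection given at the same visit. It would still stand beside one-injection qIRV groups whose whole modRNA dose is in the assessed arm.

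For Group 12 after Vaccination 2 there is no assessed site at all, and the SAP's data rules would not reveal this. On the diary, SAP 5.3.1.1 says: "The reactogenicity data are collected through the e-diary, which does not allow participants to skip the question". SAP 6.1.1.1 excludes only participants with no diary data over the 7 days, and SAP Table 4 codes a run of *no* answers as 0. An arm that was not injected would therefore be counted as having no reaction instead of as not assessed, and the result would look like a precise placebo rate.

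SAP 5.2.1.1 also provides Miettinen-Nurminen intervals for between-group differences on binary safety endpoints, with no exception for either group. Any such local-reaction difference would inherit the problem.

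The gap is confined to the prompted local-reaction items. Systemic events, the 30-minute observation, calls for severe injection-site reactions, AE collection and Group 12's Vaccination 1 rate are unaffected.

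**Working it through.** The plan gives no figure for this point, so there is nothing to reproduce. The check is a count of sites, followed by the size of the effect.

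**1. Injected sites covered by the right-arm rule (protocol Table 6)**

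| Groups | Sites injected | Sites prompted | Left out |
|---|---|---|---|
| 1, 2, 3, 4 | 2 (one per visit, both right) | 2 | none |
| 7, 8, 10, 11, 13, 14 | 1 (right) | 1 | none |
| 5, 6 | 2 at one visit | 1 | left QIV site; the modRNA site is covered |
| 9 | 2 at one visit | 1 | left bIRV 2 x A site |
| 12, Vaccination 1 | 1 (right) | 1 | none |
| 12, Vaccination 2 | 1 (left) | 0 | the only site |

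Groups 9 and 12 are the only groups in which the rule misses a modRNA site or leaves a vaccination with no assessed site.

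**2. Group 12, Vaccination 2 (120 participants, if enrolled)**

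If participants answer for the right arm as instructed, about 0 of 120 report a reaction. The Clopper-Pearson upper limit for 0/n is 1 − 0.025^(1/n). With n = 120 this is 1 − 0.025^(1/120) = 3.0%. The table would read 0% (0 to 3.0%) regardless of the rate at the placebo site.

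**3. Group 9, equal per-arm rates (assumed)**

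Let p be the rate in each arm and phi the within-person correlation. Then P(both) = p² + phi·p(1 − p) and P(either) = 2p − P(both). The shortfall of the right-arm rate is P(either) − p = p(1 − p)(1 − phi).

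| p | phi = 0 | phi = 1 |
|---|---|---|
| 20% | 0.2 × 0.8 = 16 points | 0 |
| 50% | 0.5 × 0.5 = 25 points | 0 |
| 70% | 0.7 × 0.3 = 21 points | 0 |

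At p = 50%, intermediate correlations of 0.3, 0.5 and 0.8 give 17.5, 12.5 and 5.0 points.

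**4. Group 9, unequal per-arm rates (assumed)**

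The shortfall is pL − P(both), where P(both) runs from pR·pL (independence) to min(pR, pL) (maximum overlap).

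- Right 70%, left 20%: 20 − 14 = 6 points, down to 20 − 20 = 0.
- Right 20%, left 70%: 70 − 14 = 56 points, down to 70 − 20 = 50.

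**5. Against sampling error**

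At the initial n = 15, 8/15 has a 95% CI of 27% to 79%, so the equal-rate shift lies within noise. If Group 9 is expanded to 120, 60/120 has a 95% CI of 41% to 59%. The shifts of 12.5 to 25 points at p = 50% then exceed the half-width of about 9 points, while the 5-point shift does not.

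**The case against.** The strongest reply is that this is a deliberate and disclosed scope. The right-arm rule is stated consistently, and SAP 6.1.1.1 points its estimand to SAP 3.1.1.1, which contains it. The amendment history (protocol 10.13) shows that Table 6 was added in the same amendment as Group 9, with the stated aim of assessing local reactions accurately, and per-site assessment is a legitimate convention. This shows that the restriction is defined, but the pointer only confirms that the mismatched rule is the one analysed. The amendment history also says the right arm was chosen because bIRV goes there. That reason explains Groups 5 and 6, but not leaving one of Group 9's bIRV sites unassessed.

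Several narrower points stand in part:

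- Groups 5 and 6 also have an unprompted left site (QIV). Their modRNA site is covered, so the problem is smaller, but a right-arm-only label should apply to them too.
- The documents do not say which items the diary shows when the right arm was not injected, and protocol 10.10.8.8.4 (Visit 203) refers only to the injection site. Some participants might report left-arm pain. The 0% figure is what follows from the rule as written, and a mixture of arms would be no easier to interpret.
- Group 12 is optional in the protocol, although SAP 2.3.1 says in its text that it will be enrolled. Expansion of Group 9 depends on IRC selection.
- SAP 6.1.1.1 lists no between-group difference for local reactions, and SAP 5.2 analyses initial and expanded enrollment separately. Carry-forward through SAP 5.2.1.1 is therefore possible, not certain.
- Left-arm reactions can still be recorded as AEs. That is not equivalent to daily prompting, because AE questioning is nonleading (protocol 8.3). Stopping rule 5 in protocol 10.10.8.6 also sets aside these 7-day local reactions even when they are recorded as AEs.

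**Conclusion.** The concern holds: the collection rule and Table 6 do not fit together, and the SAP would report the result without saying so.

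The site count comes directly from the documents: one of two modRNA sites is prompted in Group 9, and none of one site in Group 12 at Vaccination 2. The Group 12 arm is read from its table position, on which protocol Table 6, the protocol 1.2.2 schema and SAP Table 2 agree.

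The sizes are less firm. The 0% (0 to 3.0%) for Group 12 assumes that the group is enrolled at 120 and answers for the right arm as instructed. The 0 to 25 points for Group 9 rests on assumed equal per-arm rates. With unequal rates the shortfall depends on which site is the more reactogenic, and could be close to nothing or much larger. At 15 participants the equal-rate shift cannot be told from sampling error; at 120 it may be.

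This should be fixed because it affects a primary safety table, although no hypothesis test depends on it.

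**What to change.** Reconcile protocol 8.2.3.2, protocol 10.10.8.3, Table 6 footnote a and SAP 3.1.1.1 with Table 6, so that the diary's local-reaction items cover each arm injected at that vaccination. In SAP 6.1.1.1, report results per site and as either arm.

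Where left-arm data are not collected:

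- label all Substudy B local-reaction results as right arm only;
- footnote that Group 9's result covers one of two modRNA sites;
- report Group 12 Vaccination 2 as *not assessed* instead of 0%;
- leave both out of any between-group local-reaction differences under SAP 5.2.1.1.

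The full change costs a second set of three diary items for the affected groups, plus protocol and SAP wording. If the data are already collected, only table labels and footnotes are needed. Neither route adds visits or participants.
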